6.3.3.13 Pediatric Quality of Life Inventory (PedsQL 2.0 Family Impact Module) Scale

The PedsQL™ Family Impact Module was designed to measure the impact of pediatric chronic health conditions on parents and the family. The PedsQL™ Family Impact Module measures parent self-reported physical, emotional, social, and cognitive functioning, communication, and worry. The Module also measures parent-reported family daily activities and family relationships.

There are 6 items for Physical Functioning, 5 items each for Emotional Functioning, Cognitive Functioning and Worry, 4 for Social Functioning, and 3 for Communication. There are additionally 3 questions for Daily Activities and 5 for Family Relationships.

Each of the responses to the 36 items is initially scored on a 5 point Likert scale from 0(Never) to 4 (Almost always). Scores will be linearly transformed to a scale of 0 to 100, where 0=100, 1=75, 2=50, 3=25 and 4=0, and higher scores mean better health related quality of life. If more than 50% of the items in the scale are missing, the scale scores should not be computed. A mean score is calculated as the sum of the items over the number of items answered. If some of the answers on a scale are missing but 50% or more of the items in the scale are completed, then impute the mean of the completed items in a scale.

The Parent HRQL Summary Score (20 items) is computed as the sum of the items divided by the number of items answered in the Physical, Emotional, Social, and Cognitive Functioning scales.

The Family Functioning Summary Score (8 items) is computed as the sum of the items divided by the number of items answered in the Daily Activities and Family Relationships scales.

The Total Score is the sum of all 36 items divided by the number of items answered.

Descriptive statistics for baseline and EOS/ET will be provided for the summary scores. The change from baseline will be calculated and ZX008 and placebo groups will be compared using the same methods as specified for the PedsQL 4.0 analysis.

6.3.3.14 Clinical Global Impression – Improvement Rating, as assessed by the Parent/Caregiver

The parent/caregiver will rate their global impression of the subject's condition during Titration period (Visit 5 and Visit 6), Maintenance period (Visit 8 and 10), and at End of study (Visit 12).

The CGI-I scale measures the change in the subject's clinical status from a specific point in time, i.e., the Baseline Period. The CGI-I rating scale permits a global evaluation of the subject's

improvement over time. The severity of a patient's condition is rated on a 7-point scale ranging from 1 (very much improved) to 7 (very much worse) as follows:

1=very much improved

2=much improved

3=minimally improved

4= no change

5=minimally worse

6=much worse

7=very much worse

The mean (SD) CGI-I score, and the number and percentage of subjects who showed improvement (i.e., had a score of 3 or lower), and the number and percentage who did not improve (i.e., had a score of 4 or higher) will be presented for each for each treatment group at each assessment time point. Each assessment time point will also include a comparison between each active treatment and the placebo group using the Cochran-Mantel-Haenszel test stratified by age group, and a frequency distribution of the number and percentage of subjects in each category in the scale. A histogram of the frequency distribution will be presented.

The number and percentage of subjects who showed good or very good improvement (i.e., had a score of 2 or lower), and the number and percentage who did not improve (i.e., had a score of 3 or higher) will also be presented for each for each treatment group at each assessment timepoint as an exploratory analysis.

Individual subject CGI-I data will be listed.

6.3.3.15 Clinical Global Impression – Improvement Rating, as assessed by the Investigator

CGI-I score data assessed by the investigator will be summarized and analyzed by the same method used for CGI-I score data recorded by parent/caregiver as above.

6.3.4 Exploratory Analyses

6.3.4.1 Change from baseline in sleep quality

The parent/caregiver will be asked to indicate the appropriate response that adequately describes their child's sleep quality since starting IMP at Titration period (Visit 6), Maintenance period (Visit 8 and 10), and at End of study (Visit 12). The following question will be asked:

Since your child has started taking the study medication in this study, have you noticed that s/he has been waking in the middle of the night or very early in the morning more than usual?

The response will be noted as below-

- My child's sleep is more disturbed than it was before s/he started the study medication
- My child's sleep patterns are the same as they were before starting the study medication
- My child sleeps better than s/he did before starting the study medication

For each time point, the number and % of subjects in the response categories will be presented, by treatment group.

All sleep quality assessment data will be presented in the subject data listing.

6.3.4.2 Change from baseline in meal time behavior

The parent/caregiver will be asked to indicate the appropriate response that adequately describes their child's eating behavior since starting IMP at Titration period (Visit 6), Maintenance period (Visit 8 and 10), and at End of study (Visit 12). The following question will be asked:

Since your child has started taking the study medication in this study, have you noticed that s/he has had a change in their meal time behavior?

- My child has worse meal time behavior since starting the study medication
- My child's meal time behavior has not changed since starting the study medication
- My child has improved his/her meal time behavior since starting the study medication

For each time point, the number and % of subjects in the response categories will be presented, by treatment group.

6.3.4.3 Change from baseline on Karolinska Sleepiness Scale

The Karolinska Sleepiness Scale will be administered according to the schedule visit time points in [Table 1](#). The Karolinska Sleepiness scale is a self-report scale that measures the subject's drowsiness. It is a 9-point verbally anchored scale, which ranges from 'extremely alert' at one end of the scale to 'extremely sleepy – fighting sleep' at the other end of the scale. Within this study, the scale will be completed by the observer in an exploratory manner.

Score	Description
1	Extremely alert
2	Very alert
3	Alert
4	Rather alert
5	Neither alert nor sleepy
6	Some signs of sleepiness
7	Sleepy, but no effort to keep awake
8	Sleepy, some effort to keep awake

9

Very sleepy, great effort to keep awake, fighting sleep

Descriptive statistics will be presented for each time point where measured and will include number and percent of subjects in each category, mean, standard deviation, median, minimum and maximum. The ZX008 0.5 mg/kg/day and placebo groups will be compared on change from baseline using a Wilcoxon rank sum test.

Additionally, scores of 1-6 will be categorized as “Active” and scores of 7-9 categorized as “Sleepy”. These categorizations will be summarized using counts and percent (%) of subjects by treatment by each visit time point. A Fisher’s exact test will compare the proportion of subjects reporting sleepy scores (7, 8 or 9) in the ZX008 0.5 mg/kg/day to the analogous proportion in the placebo group.

All Karolinska Sleepiness data will be presented in the subject data listing.

6.3.4.4 Assessment of a Dravet Syndrome Composite Endpoint

As stated in the protocol, a Dravet syndrome composite endpoint will be created using outcome measures from the protocol to create a composite endpoint to assess treatment of Dravet syndrome without emphasis on a single endpoint. The outcomes under evaluation in this study will include measures for example such as seizure frequency, behaviour, quality of sleep, and others. The measures to select the composite are identified as part of a project with physician interviews and interviews with patient’s families and are part of a project on multi-dimensional outcome measures discussed in the protocol. A separate SAP will be developed to describe the exploratory analyses that test the psychometric development and performance (or measurement accuracy) of the core outcome measures for the composite endpoint and the results will be reported separately.

6.4 SAFETY ANALYSES

All safety analyses will be performed for the Safety population (SAF) and will be reported by treatment group, and overall.

6.4.1 Adverse Events

An AE is defined as any unfavorable and unintended sign (including an abnormal, clinically significant laboratory finding), symptom, or disease temporally associated with the use of a medicinal (investigational) product, whether or not considered related to the medicinal (investigational) product. The period of observation for adverse events extends from the time the subject gives informed consent until the end of the titration/transition period (Visit 13). For patients who continue into the open-label extension study, AEs of special interest will continue to be monitored for up to 6 months after the last dose of study medication.

A TEAE is defined as any AE that based on start date information occurs after the first intake of study treatment. All other AEs occurring after enrollment and prior to the first administration of study treatment are defined as non-treatment emergent AEs (non-TEAEs).

Any missing relationship will be considered as “related.”

The severity of AEs (whether non-serious or serious AEs) will be assessed by the investigator as follows:

Severity Definition of Adverse Events:

Mild - A type of AE that is usually transient and may require only minimal treatment or therapeutic intervention. The event does not generally interfere with usual activities of daily living.

Moderate - A type of AE that is usually alleviated with additional specific therapeutic intervention. The event interferes with usual activities of daily living, causing discomfort but poses no significant or permanent risk of harm to the research participant.

Severe - A type of AE that interrupts usual activities of daily living, or significantly affects clinical status, or may require intensive therapeutic intervention.

Any missing severity will be imputed as “severe.”

The original terms used by the investigators in the eCRFs to identify AEs will be coded using the most recent version of the MedDRA implemented by the sponsor at the end of the study.

6.4.1.1 Overview of Events:

The number and percent of patients with at least one of the following events will be summarized in an overall summary table:

- TEAE.
- Serious TEAE
- Related TEAE
- Related serious TEAE.
- TEAE leading to treatment discontinuation
- Death

The percentage denominator for the calculation of percentage will be the number of subjects in the SAF.

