8. ADVERSE EVENTS

8.1 DEFINITIONS

8.1.1 Adverse Events

According to ICH guidelines, an AE is any untoward medical occurrence in a patient or clinical investigation subject administered a pharmaceutical product and which does not necessarily have a causal relationship with this treatment. An AE can, therefore, be any unfavorable and unintended sign (including an abnormal, clinically significant laboratory finding), symptom, or disease temporally associated with the use of a medicinal (investigational) product, whether or not considered related to the medicinal (investigational) product. The period of observation for adverse events extends from the time the subject gives informed consent until the end of study.

Adverse events may include:

- Exacerbation (ie, an increase in the frequency or severity) of a pre-existing condition. Illness present before study entry should be recorded in the medical history section of the eCRF and only be reported as an AE if there is an increase in the frequency or severity of the condition during the study. Exacerbation of seizures is considered an AE if there was an increase in frequency beyond the subject's typical pre-study fluctuations, or in the event that seizures lengthen in duration in a clinically meaningful way compared with baseline, or if a new seizure type emerges.
- A clinical event occurring after consent but before IMP administration.
- Intercurrent illnesses with an onset after administration of IMP.

Adverse events do not include:

- Medical or surgical procedures (the condition that leads to the procedure is the AE, eg, tonsillitis is the AE if a tonsillectomy is performed)
- Situations where an untoward medical occurrence has not taken place. For example:
 - Planned hospitalizations due to pre-existing conditions, which have not worsened.
 - Hospitalizations that occur for procedures not due to an AE (eg, cosmetic surgery).

- Hospitalizations for a diagnostic procedure where the hospital stay is less than 24 hours in duration or for normal management procedures (eg, chemotherapy).

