9. DATA HANDLING PROCEDURES

9.1 RECORDING OF DATA

The investigator (or delegate) will maintain individual records for each subject. These records should include dates when a subject visited the study site, study-required information and data, and other notes as appropriate. These records constitute source data.

An eCRF and a subject diary will be provided by the Sponsor (or delegate) for each subject enrolled into the study. Study site staff will enter data directly into the validated electronic data capture (EDC) system by completing the eCRF via a secure internet connection. The investigator is responsible for ensuring accurate and proper completion of the eCRF and subject diary for recording data according to the instructions given in the eCRF and subject diary.

All entries in the eCRF must be backed up by the relevant source data at the study site. All source data will be kept according to all applicable regulatory requirements (see [Section 12.8](#)). Source data must be completed legibly for each subject enrolled into the study and signed by the investigator (or delegate).

Data entry in the eCRF and subject diary must be completed in a timely manner so that they always reflect the latest observations on the subjects enrolled in the study.

The subject's diary will be completed by the parent/caregiver at home. Data entries will be reviewed by the investigator for completion and consistency.

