6.4.1.2 Treatment Emergent Adverse Events

The following summaries will display the number and percentage of subjects with adverse events by system organ class (SOC) and preferred term (sorted alphabetically) for each treatment group and overall:

- All TEAEs

- Serious TEAEs
- TEAEs by Maximum Severity
- Study Drug Related TEAEs
- All AEs that lead to premature discontinuation from the study

An additional summary will tally the number and percent of subjects in each treatment group who experience an AE that occurs in at least 5% of subjects. The summary will be presented by preferred term in decreasing order of incidence.

The summaries will be provided for the double-blind treatment period. No inferential statistical methods (i.e., methods that yield p-values) will be used to compare treatment groups on the frequency or severity of AEs.

Additionally, the following listings will be produced for all enrolled subjects:

- All AEs, events considered to be TEAE will be identified in the listing
- Serious AEs
- AEs that lead to premature discontinuation from the study
- Deaths

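### SAP 6.4.1 defines a TEAE by start date alone, so a baseline-onset AE that worsens on study drug drops out of the by-arm TEAE tables if the site keeps it as one record

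*SAP*

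**What the plan says.** SAP 6.4.1 gives the only operative definition: "A TEAE is defined as any AE that based on start date information occurs after the first intake of study treatment". Its next sentence classes AEs that occur after enrollment but before first administration as non-treatment-emergent, with no exception for later worsening.

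Protocol 8.4 starts AE collection at informed consent. Protocol 8.1.1 lists among adverse events "A clinical event occurring after consent but before IMP administration" and also "Exacerbation (ie, an increase in the frequency or severity) of a pre-existing condition". Its recording instruction is narrower: "Illness present before study entry should be recorded in the medical history section of the eCRF", to be reported as an AE only if it worsens during the study. Protocol 9.1 says the eCRF is completed "according to the instructions given in the eCRF and subject diary"; those instructions are not among the documents.

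SAP 6.4.1.2 plans by-arm summaries of all, serious, maximum-severity and drug-related TEAEs, and one of "All AEs that lead to premature discontinuation from the study". It plans no p-values for AEs. Among the listings it includes "All AEs, events considered to be TEAE will be identified in the listing".

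**The concern.** A definition of treatment emergence normally has two limbs: new onset after first dose, and worsening after first dose of something already present. SAP 6.4.1 has only the first. A child whose mild baseline AE becomes severe or serious on study drug could then be absent from the tables meant to show on-treatment harm. With no formal comparison of AEs, readers will rely on those by-arm counts. Whether such an event is counted would depend on whether the site opens a second record.

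The omission also sits oddly with the rest of the SAP, which is conservative elsewhere. A missing relationship becomes related, a missing severity becomes severe (both 6.4.1), and an AE that might have started after first dose is treated as a TEAE (6.1.7).

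**Working it through.** There is no plan figure to reproduce. The check is a reading of the rules, plus a count of where they apply.

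**1. Can an AE be open at first dose?** Yes. Collection starts at consent (Protocol 8.4), the Baseline Period lasts 6 weeks (Protocol 3.1), and AEs are recorded at Visits 1, 2 and 3 before dosing (Protocol 6.2.2 to 6.2.4).

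**2. Does any other section add a worsening clause?** No. SAP 6.1.7 concerns missing dates and works from start and end dates only. SAP 6.4.1.2 and 6.9 and Protocol 10.5.2 add nothing.

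**3. Does the protocol require a new record on worsening?** Not for an AE that began after consent. The 8.1.1 instruction concerns illness present before study entry. Section 8.5.1 asks for follow-up of an AE until it resolves or stabilizes, which fits one continuing record. Section 8.6.1 foresees an ongoing AE becoming serious after the observation period and points to 8.9, which does not call for a new entry.

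**4. The rule applied to a hypothetical case.** A mild AE is recorded at Visit 2 (Day -21), is ongoing on Day 1, and is severe and serious by Visit 6 (Day 22).

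| Site practice | Start date used | Class | By-arm all, serious and maximum-severity TEAE tables | All-AE and SAE listings |
|---|---|---|---|---|
| One continuing record | Before Day 1 | Non-TEAE | Absent | Present |
| New record at worsening | After Day 1 | TEAE | Counted | Present |

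**5. Where the flag applies.**
- Appendix 1, section 14.3.1: 14.3.1.1b to 14.3.1.8b are restricted to TEAEs by title; 14.3.1.9b (AESI by SOC and PT) is not. That is 8 of 9.
- Section 14.3.2 has three more entries labelled as tables (deaths, SAEs, discontinuations due to AE). They are listings by title and not TEAE-restricted. Counting them gives 8 of 9 + 3 = 12.
- SAP 6.4.1.1: 5 of 6 overview rows are TEAE rows; death is the exception.
- SAP 6.4.1.2: 4 of the 5 bulleted SOC/PT summaries are TEAE-restricted; the discontinuation summary is the exception. The further 5% incidence summary is worded for AEs in the text, while shell 14.3.1.7b is restricted to TEAEs.

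**6. Scale.** One omitted child moves an arm's incidence by 1/45 = 2.2 percentage points at the protocol's arm size, or 1/40 = 2.5 points at the SAP's. This is the weight of one child, not an estimate of how many are affected.

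**7. First-dose day.** SAP 6.1.7 moves some partial or missing start dates to the first-dose date so that the event counts as a TEAE. The definition in 6.4.1 covers onset after first intake, and its complement covers onset before first administration. An AE known only to start on that day is in neither class.

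**8. Discontinuation.** SAP 6.4.1.2 summarizes all AEs leading to study discontinuation; shell 14.3.1.3b restricts the same summary to TEAEs. Both cannot be followed. The 6.4.1.1 row counts TEAEs leading to treatment discontinuation, a different event.

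**The case against.** The strongest reply is that the harm depends on a document nobody here can see. If the eCRF instructions call for a new entry on worsening, the present rule counts the event and nothing is lost. The protocol leans that way in places: exacerbation is listed as an AE in its own right, worsening seizures have their own criterion (8.1.1), and status epilepticus episodes go into the AE log (8.1.2). What remains is an AE opened between consent and first dose, still open, worsening on drug and not re-entered. The eligibility review at Visit 3 narrows this further. All of that stands, and it is why the consequence is conditional.

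The related-event table is also a weaker example than the others. Protocol 8.3 calls an event related when it follows study-drug administration in a reasonable time sequence. A record dated before dosing does not fit, and an investigator who attributes worsening to the drug has reason to open a new record. That stands too.

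Other outputs soften the effect. Deaths in the overview are not limited to TEAEs, status epilepticus recorded as an AE is tabulated for baseline and T+M (SAP 6.3.3.8), and laboratory and vital-sign data are analyzed as change from baseline. None of this gives a by-arm count of baseline AEs that worsen.

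**Conclusion.** The gap in SAP 6.4.1 is real and nothing elsewhere in the documents closes it. If a site keeps one record, on-drug worsening of a baseline AE is left out of the TEAE-restricted by-arm tables. Confidence is high on the wording and moderate on the consequence, because recording practice is unknown. The point merits consideration and does not touch efficacy, alpha or sample size.

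A reader might infer three stronger things that the documents do not support:
- **That these events vanish from the report.** They do not; the all-AE listing and the SAE listing (14.3.2.2b) would show them.
- **That nearly every AE table in Appendix 1 is affected.** The 8 of 9 holds for section 14.3.1 only.
- **That the active arm is undercounted.** If the drug caused worsening, the omission would fall more on that arm, but the documents give neither the number of such events nor any difference between arms.

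**What to change.** Amend SAP 6.4.1 so that a TEAE is *an AE with onset on or after the first dose (unless recorded as starting before that dose), or an AE present before first dose that increases in severity or becomes serious on or after it*. The first limb also settles AEs dated or imputed to the first-dose day.

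Before unblinding, query AEs that were open at first dose, so that any worsening held inside a single record can be dated and classed. The queries are needed because the documents do not show that dated severity changes within a record are captured.

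Separately, make the 6.4.1.2 study-discontinuation summary and shell 14.3.1.3b agree by using all AEs in both. Keep the 6.4.1.1 row on treatment discontinuation as its own item, since stopping drug and leaving the study are different events.

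The cost is one SAP sentence, one shell title and one round of queries. TEAE counts may rise slightly. Because the tables count subjects, a continuing event held in two records does not count a child twice within a term.
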